2.2.2 Measuring Fidelity and Model Components

In order to answer the main research question in Aim 1, it is crucial to have accurate knowledge about the type of care model present in each study clinic at the time the Primary Cohort began care coordination. It is also important to know how that model has changed since 2018 when the Historical Cohort was beginning to receive care coordination, during the pandemic in 2020, and whether any changes are planned during the post-coordination year for the Primary Cohort. Therefore, we will

employ the three strategies in **Table 1** to ascertain and confirm both the overall model used, and the core functions/components of care coordination delivery at each clinic throughout this time. These data will allow us to characterize both fidelity to the overall model and the specific ways in which there is variation within and between both models at the level of individual clinics. Timing of the patient cohorts and data collection efforts is illustrated in **Figure 1**.

Table 1: Strategies for Measuring and Accounting for Fidelity to Each Care Coordination Model

Strategy	Description	Sample Size	Expected Response Rate	Timeframe
1	Care Coordinator Survey	~300-400	100% (required)	Q1 2022
2	Organizational Survey	~50-70	100% (required)	Q3 2021
3	Primary Cohort Patient Survey	~7,000 (~20/clinic)	60%	Q3 2022

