The second strategy for measuring fidelity to each care coordination is to supplement our understanding of care coordination delivery at each clinic through surveys at the overall organizational level in the fall of 2021. Although the care coordinator survey will be the primary source of the specifics of care coordination, we will ask organizational leaders a broader set of questions to better understand the context, intent, resource support, and overarching design of care coordination within which each clinic system implements its modifications and refinements. A clear and detailed understanding of these factors will be fundamental to our Aim 3 analysis, but where overlap in data collection exists, it will help to clarify aspects of our Aim 1 and Aim 2 analyses as well. These surveys will also provide insight into the effect of COVID on coordination policies and processes as well as any plans for changes in the coordination approach through the end of our study.

The third strategy is a survey of care coordination patients from our primary cohort. This will occur in the fall of 2022 and will be incorporated in our planned second patient survey. The primary goal of the

patient surveys is to obtain patient-reported outcome measures for our comparative analyses. A secondary goal, applicable mainly to the primary cohort, will be to ask patients how they experienced the various components of care coordination, which we can then compare with the designated care coordination model. In cases where we see a pattern of divergence in accounting for fidelity, we will follow-up with clinic staff to further clarify these details. In this way, patient-level interactions will provide additional insight into care coordination model fidelity. Patient surveys will not be used this purpose for the Historical cohort due to the difficulty in patients recalling events or situations that occurred years ago. Instead, that survey will focus mainly on understanding COVID-19 impacts on these multi-morbidity patients' health and healthcare.

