4.4.2.2 Patient Survey Sampling and Recruitment (Historical and Primary Cohorts)

Patient surveys will be conducted once for each of the Historical and Primary patient cohorts. A total of 3,000 patients in the Historical Cohort and 7,000 patients in the Primary cohort will be sent surveys, with an expected response rate of 60% (yielding approximately 1,800 and 4,200 responses respectively).

Survey recipients will be selected randomly. Clinics contributing small numbers of patients may be oversampled to ensure adequate representation. MNCM will provide CESR with the name, contact information, and home clinic of the sampled patient list through a secure data transfer for each cohort.

CESR will manage patient survey recruitment and data collection. CESR will mail the survey invitation to patients with a \$2 non-contingent token incentive. A web survey link and personalized PIN will be sent with a cover letter co-signed by the patient’s home clinic as well as the study PIs. Initial non-responders will be called by CESR staff at various times of the day and days of the week to maximize the probability of successful contact and survey completion. Patients completing the survey will receive a small (e.g., \$10-\$20) retail gift card as a thank you for their time. Recruitment will continue until the contact protocol specified in Section 5.4.4 has been exhausted.

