7.3.6 Causal Inference

7.3.6.1 Causal model underlying the research question

[figure not shown]
The primary causal research question(s) of interest in this study is, “What is the difference in risk/probability of outcome Y for care coordination patients under the medical/social model, versus the risk/probability of outcome Y for care coordination patients under the nursing/medical model,” where Y refers to each of the designated study outcomes (quality measures, utilization, patient-reported measures). Analyses will align with the following representation of the PICOTS framework: (1) the study *population* will consist of care coordination patients in participating Minnesota primary care clinics meeting criteria for the Historical or Primary Cohorts (as described in Section 4.2.2); (2) the study *intervention* is delivery of care coordination services to high-cost/high-need patients in primary care; (3) primary *comparators* will be the medical/social model versus the nursing/medical model for delivering care coordination, which have been implemented at the clinic level; (4) several care quality measures (e.g., proportion of patients with diabetes under control), healthcare utilization measures (e.g., hospitalizations), and patient-reported measures (e.g., health status) will be independently evaluated as study *outcomes*; (5) *timing* of the source data for health care quality and utilization measures will be based on the 12 months preceding and 12 (up to 36 for Historical cohort) months following each patient’s initiation of care coordination services (i.e., to account for the pre-to-post change in outcomes at the individual level upon exposure to the intervention) and patient-reported outcomes will be obtained by survey 6-18 months after initiation of care coordination services; and (6) the *setting* will be care coordination programs in Minnesota area clinics, with study data being drawn from electronic health records (as collected and combined from clinics statewide by MN Community Measurement), insurance claims, and patient surveys.

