7.3.6.2 Population used to generate effect estimates

As described in Section 4.2.2, patients will be eligible for analyses if they have been designated for care coordination at a participating clinic and have not opted out of research. For utilization outcomes, inclusion will additionally require health insurance coverage from a participating payor. For patient-reported outcomes, inclusion will additionally require completion of the study survey. As described above, patients will be followed for health care quality and utilization outcomes over the 12 months preceding and the 12-36 months following the first observed enrollment in care coordination, and patient-reported outcomes will be collected by survey in the 6-18 months following first enrollment in care coordination (Primary Cohort only). For a discussion of analytic implications of selection by survey response, please see Section 7.3.6.1 above. Differences in survey respondents vs. non-respondents will be assessed for potential selection bias and potential impact on validity of results.

7.3.6.3 Timing of the outcome assessment relative to the initiation and duration of exposure

As described above, timing in the assessment of health care quality and utilization outcomes will account for outcomes in the 12 months preceding initiation of care coordination in comparison to outcomes in the 12 months following initiation of care coordination. Assessment of patient-reported outcomes will be collected in the 6-18 months following initiation of care coordination (Primary Cohort only). Patients' exposure time will be the observable duration of time spent in a care coordination program; they will be considered exposed for the entire follow-up period for each outcome. Exposure to the intervention (care coordination) will be determined at the patient level, whereas comparator status (choice of care coordination model) will be implemented by each clinic at the clinic level. Due to these conditions, sequential temporality will be ensured, and immortal time bias will not be applicable.

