7.3.6.4 Potential confounders

For primary analyses, covariates will be measured at or prior to baseline (entry into care coordination). Patient-specific follow-up duration (i.e., 6-18 months) for patient-reported outcomes collected by survey will be accounted for as a covariate. Section 7.3.6.1 also describes how potential confounders will be specified and addressed.

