9.1.4 Sensitivity of inferences to missing data methods and assumptions

Given the primary and sensitivity analyses described above, we will accumulate empirical evidence on the potential impact of differential (informative) missingness on our results. We intend to maintain transparency and report all results accordingly. Interpretations based on our findings will be presented in the context of our assessments of missing data.

10 Key Study Milestones

The select dates below represent the expected data collection timeline and is subject to change. Legally contracted study milestones are included in the HPI contract with PCORI and are closely monitored by the PCORI Program Office.

Historical Cohort Data Collection	Expected completion date
Historical Cohort data submission from clinics to MNCM	Sep 15, 2021
Historical Cohort patient interviews	Aug 15, 2021
Historical Cohort patientIDs verified with payors (multi-step process)	Nov 30, 2021
Historical Cohort patient surveys	Dec 15, 2021
Historical Cohort utilization data assembled and returned to MNCM	Dec 31, 2021

Preliminary Historical Cohort dataset assessment
 Final Historical Cohort dataset available for analysis

June 1, 2022
 July 1, 2022

Primary Cohort Data Collection

Primary Cohort data submission from clinics to MNCM	June 15, 2022
Primary Cohort patient interviews	April 15, 2022
Primary Cohort patientIDs verified with payors (multi-step process)	Aug 31, 2022
Primary Cohort patient surveys	Nov 15, 2022
Primary Cohort utilization data assembled and returned to MNCM	May 1, 2023*
Preliminary Primary Cohort dataset assessment	Aug 1, 2023
Final Primary Cohort dataset available for analysis	Nov 1, 2023

**Time gap is for utilization data to accrue for approximately 12 months from date of CC enrollment*

Other data collection

Organizational survey and clinic descriptors table	Nov 1, 2021
Care Coordinator and Clinician/Leader Interviews (Phase 1)	Oct 1, 2021
Care Coordinator Survey	April 15, 2022
Patient, Care Coordinator, and Clinician/Leader Interviews (Phase 2)	Dec 31, 2023

Analysis and Dissemination

All data analyses complete for all study aims	April 30, 2024
Draft Final Research Report submitted to PCORI	June 30, 2024

11 Study Team Organization

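### The stated follow-up does not match the Primary Cohort's dates: survey outcomes run past 18 months, the clinic files stop short of 12 months for BMI, and Section 5.1.2 gives outdated quality years

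*Combined protocol and SAP*

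**What the plan says.** **Survey outcomes.** Table 3 lists every patient-reported outcome at 6 to 18 months. Two of them are primary: general health status and the rating of the primary care clinic. Section 7.3.6.1 repeats that "patient-reported outcomes will be obtained by survey 6-18 months after initiation of care coordination services", and Section 7.3.6.2 that "patient-reported outcomes will be collected by survey in the 6-18 months following first enrollment in care coordination". Section 7.3.6.4 adds: "Patient-specific follow-up duration (i.e., 6-18 months) for patient-reported outcomes collected by survey will be accounted for as a covariate".

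**Survey dates.** Start dates run from 1 January to 31 December 2021 (Section 4.2.2, Appendix A). Table 1 in Section 2.2.2 puts the "Primary Cohort Patient Survey" in Q3 2022. The text of the same section says of it: "This will occur in the fall of 2022 and will be incorporated in our planned second patient survey". Section 10 expects completion of the "Primary Cohort patient surveys" by 15 November 2022. The sampling frame comes from the clinics' submissions: "MNCM will provide CESR with the name, contact information, and home clinic of the sampled patient list" (Section 4.4.2.2).

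**Clinic files.** Table 3 lists A1c, blood pressure and BMI with 12 months of follow-up, from MNCM quality measures and clinic data. Appendix A, Files 3 to 5 (HbA1c, blood pressure, height and weight), run from 1 January 2020 to the date of the data pull. Submission is from 15 March to 15 May 2022. Section 10 gives 15 June 2022 for "Primary Cohort data submission from clinics to MNCM". Section 5.1.1 describes one submission round per cohort.

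**Quality years.** Section 5.1.2 gives 2017–2019 for the Historical Cohort and 2019–2021 for the Primary Cohort. Appendix B says that measurement years 2017–2022 were collected, to cover pre and post periods for both cohorts.

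**The concern.** A cohort that enrols over 12 months and is surveyed at one calendar time has follow-up spread over 12 months. A window that is itself 12 months wide then fits on one date only, and every later response pushes the earliest starters past the upper limit. Section 7.3.6.1 makes timing a formal element of the causal question, so a wrong window misstates what the two primary survey estimates describe.

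The clinic files raise the same problem in the other direction. A patient who starts late in 2021 cannot have a 12-month value in a file that closes in spring 2022. Section 9.1.2 excludes patients with a missing outcome but does not say whether an earlier value may stand in for a 12-month one. Section 9.1.1 reads an absent entry in the care quality database as care that was not given. Applied to file-based outcomes, that rule could turn the end of an extract into apparent care gaps.

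In Section 5.1.2, the end year of 2021 sits badly with a 12-month outcome in patients who start during 2021.

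**Working it through.** **Inputs.** Start dates are 1 January to 31 December 2021, which is 365 start days. Survey dates come from Table 1, Section 2.2.2 and Section 10. File end dates come from Appendix A and Section 10, with the pull date taken as the submission date. The documents give no monthly accrual, so even enrolment over 2021 is an assumption.

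**1. The plan's own window.** On 1 July 2022 the first starter is at 17.9 months and the last at 6.0 months. The stated 6 to 18 months is reproduced on that date.

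**2. Survey on later dates.** A start day counts as late if its 18-month anniversary falls before the response date.

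| Response date, 2022 | Time since start (months) | Start days past 18 months | Share |
|---|---|---|---|
| 1 July | 6.0–17.9 | 0 of 365 | 0% |
| 1 September | 8.0–20.0 | 59 of 365 | 16% |
| 30 September | 9.0–20.9 | 88 of 365 | 24% |
| 15 November | 10.5–22.4 | 134 of 365 | 37% |

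Nobody is below 6 months on any of these dates, so only the upper limit is wrong.

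These shares treat all responses as arriving on one day. Section 5.4.4 describes a mailed invitation, then up to six calls starting about two weeks later, so responses will spread. Averaging the daily share over a fielding period (even response is a second assumption) gives:

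- 1 July to 30 September (Table 1): 12%
- 1 July to 15 November: 18%
- 1 September to 15 November (one reading of fall 2022): 27%

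**3. Clinic files.** Twelve months is reached if the 12-month anniversary falls on or before the pull date.

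| Pull date, 2022 | Follow-up in files (months) | Start days with 12 months | Share with | Share without |
|---|---|---|---|---|
| 15 March | 2.4–14.4 | 74 of 365 | 20% | 80% |
| 15 May | 4.4–16.4 | 135 of 365 | 37% | 63% |
| 15 June (Section 10) | 5.5–17.4 | 166 of 365 | 45% | 55% |

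With Section 7.2.1's 397 clinics × 57 patients = 22,629, the numbers with 12 months in the files are 22,629 × 74/365 ≈ 4,590 to 22,629 × 166/365 ≈ 10,290, before missing values. A pull earlier than 15 March would lower them.

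**4. Which outcomes depend on the files.** Appendix B has no BMI measure, so no described source takes BMI to 12 months for most patients. For A1c and blood pressure, MNCM measurement year 2022 covers the 12-month anniversary of patients aged 18–75 in the diabetes measure (both) or the vascular measure (blood pressure). The files would matter for these outcomes only in patients outside those measures.

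**5. Quality years.** Data ending on 31 December 2021 would give all 365 Primary Cohort start days less than 12 months. Data ending on 31 December 2019 would cut off 59 of 424 Historical start days (14%), those in January and February 2019. With 2022 included, as in Appendix B, every Primary Cohort patient reaches 12 months.

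**6. Power of an analysis limited to 18 months.** Section 7.2.1 gives SD 10, ICC 0.01, a 45/55 split, 80% power and two-sided 5%, with 60% of 7,000 = 4,200 responses. Detectable difference = 2.80 × 10 × √[DE × (1/0.45n + 1/0.55n)], with DE = 1 + (n/397 − 1) × 0.01.

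- n = 4,200: DE = 1.096, difference 0.91 points
- n = 4,200 × 0.816 = 3,428 (18% removed): DE = 1.076, difference 1.00 points

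**The case against.** The strongest reply is that little turns on this. Section 7.3.6.4 adjusts for each patient's own follow-up whatever its length, Section 10 calls its dates expected and subject to change, and Section 7.1 allows definitions to be modified if data fall short. Much of that stands. With duration in the model, a reader who infers bias between the two care models goes further than the documents allow. But permission to revise is not a revision, and Section 7.3.6.4 itself restates 6 to 18 months.

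A reader might also infer that a quarter to a third of survey responses fall outside the window. That rests on every response arriving on one late date; spread responses give 12% to 27%.

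For the files, a reader might infer that the primary quality composite lacks 12-month data, since A1c control and blood pressure control are marked as components. The documents do not support this: Table 3 gives MNCM quality measures as the composite's source, and the plan does not say that file values enter it. Nor does it say that A1c or blood pressure will be analysed in patients outside the MNCM measures. Appendix A presents the files as adding data points for three quality measures, and Table 3 limits A1c to patients with diabetes.

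For Section 5.1.2, it is tempting to conclude that no Primary Cohort patient has 12 months of quality data. That section refers the reader to Appendix B, which says in the past tense that 2022 was collected. This is a conflict of text, not a shown gap in data.

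**Conclusion.** The point holds as three mismatches between stated follow-up and dates.

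1. The 6 to 18 months stated for the Primary Cohort survey outcomes, two of them primary, is wrong at its upper end. The documents' dates imply about 6 to 21 months for Q3 fielding and up to about 22.5 months by 15 November 2022. The share beyond 18 months is about 12% to 27%, and at most 37%, given even enrolment and, for the lower range, even response.
2. A 12-month BMI result would rest on files that reach 12 months for about 20% to 45% of starters, taking the pull date as 15 March to 15 June 2022. The same limit would apply to A1c or blood pressure results based on the files alone, if any are planned. The number of such patients is not given.
3. Section 5.1.2 needs updating to agree with Appendix B.

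No primary comparison is shown to change. Utilization is not affected: claims are due on 1 May 2023, 16 months after the last start. The weight lies between a minor point and one that should be fixed, mainly because two primary outcomes carry an incorrect time label.

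**What to change.** - **Survey.** Restate the window in Table 3 and Sections 7.3.6.1, 7.3.6.2 and 7.3.6.4 to match the actual field dates, up to about 22 months. Keep time since start as a covariate. A sensitivity analysis limited to 18 months is optional; with 18% of responses removed, the detectable difference on the health score rises from about 0.9 to about 1.0 points.
- **Clinic files.** Limit the 12-month BMI result, and any A1c or blood pressure result based on the files alone, to patients whose pull date allows 12 months. Otherwise relabel it with the follow-up available. State whether File 3 and File 4 values enter the composite. State also that values after the extract are unobserved and that Section 9.1.1's rule on absent documentation does not apply to them.
- **Quality years.** Align Section 5.1.2 with Appendix B: add 2022 for the Primary Cohort and 2020 for Historical patients who started in January or February 2019.

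The cost is wording, one restriction or label and, if wanted, one sensitivity analysis. The downside is a wider stated survey window and fewer patients in any 12-month BMI result.

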7.3.6.2 Population used to generate effect estimates

As described in Section 4.2.2, patients will be eligible for analyses if they have been designated for care coordination at a participating clinic and have not opted out of research. For utilization outcomes, inclusion will additionally require health insurance coverage from a participating payor. For patient-reported outcomes, inclusion will additionally require completion of the study survey. As described above, patients will be followed for health care quality and utilization outcomes over the 12 months preceding and the 12-36 months following the first observed enrollment in care coordination, and patient-reported outcomes will be collected by survey in the 6-18 months following first enrollment in care coordination (Primary Cohort only). For a discussion of analytic implications of selection by survey response, please see Section 7.3.6.1 above. Differences in survey respondents vs. non-respondents will be assessed for potential selection bias and potential impact on validity of results.

7.3.6.3 Timing of the outcome assessment relative to the initiation and duration of exposure

As described above, timing in the assessment of health care quality and utilization outcomes will account for outcomes in the 12 months preceding initiation of care coordination in comparison to outcomes in the 12 months following initiation of care coordination. Assessment of patient-reported outcomes will be collected in the 6-18 months following initiation of care coordination (Primary Cohort only). Patients' exposure time will be the observable duration of time spent in a care coordination program; they will be considered exposed for the entire follow-up period for each outcome. Exposure to the intervention (care coordination) will be determined at the patient level, whereas comparator status (choice of care coordination model) will be implemented by each clinic at the clinic level. Due to these conditions, sequential temporality will be ensured, and immortal time bias will not be applicable.

